Secondary Aim (4): Does location of the peripheral intravenous catheter placement affect the pain that adult patients experience with peripheral IV cannulation?

D. Enrollment and Withdrawal

D.1 Inclusion Criteria

1. **Describe the criteria that define who will be included in the study as a numbered list:**

1. Adults ages 18 to 99
2. Non-pregnant women and men
3. Adults that are able to consent
4. Patients requiring intravenous catheter insertion for their operation/procedure

D.2 Exclusion Criteria

1. **Describe the criteria that define who will be excluded in the study as a numbered list:**

1. Patients with Raynaud's syndrome, sickle cell disease, and/or extreme sensitivity to cold
2. Patients with a break or an abrasion on the skin where the Buzzy device would be placed
3. Patients with nerve damage affecting the extremity where the peripheral intravenous catheter would be placed

2. **Describe in detail how the eligibility criteria will be assessed and satisfied (e.g., medical record review, physical examination):** Based on the pre-operative history and physical exam performed by the CA-1 (PGY-2) anesthesiology resident (co-investigator of study).
3. **State who will determine eligibility. Note that those who are designated to determine eligibility must have appropriate training, expertise, and oversight, for example a physician PI or Co-I on a biomedical**

study: PI (anesthesiology attending) and Co-I (CA-1 (PGY-2) anesthesiology resident). These will be the physicians who will be taking care of these subjects.

4. **Can study subjects participate in another research study while participating in this research study:**
 Yes No

D.3 Withdrawal of Subjects

1. **Describe anticipated circumstances under which subjects will be withdrawn from the research without their consent:** None
2. **Describe procedures that will be followed when subjects withdraw or are withdrawn from the research, including the possibility of partial withdrawal from study intervention with continued data collection:**
There will be no partial withdrawal from the study. Either the patient will take part in the study, which is just for the duration of the peripheral intravenous catheter insertion and the questionnaire that will take place before and after the procedure, or the patient will not take part in the study.
3. **Describe any necessary safety precautions to be applied to subjects who withdraw or are withdrawn (tapering drug doses, evaluative x-ray, etc.):** or N/A

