whether the patient may be interested in learning more about the study and potentially partaking in the study. If the patient says yes, then the Co-I will go over the consent form with the patient and explain that if the patient chooses to partake in the study, then he/she will randomly receive either the Buzzy® device or the numbing injection. The Co-I will answer any questions that the patient may have. If the patient consents to partaking in the study, then the Co-I will follow the randomization sheet with which pain-relieving technique to be administered to the patient. The Co-I will administer the appropriate technique and place the peripheral intravenous catheter.

Specifics of how the two interventions will be performed:

Experimental group - *Buzzy® device*: Subjects in this group will have the Buzzy® device applied to them. The Buzzy® consists of two components: (1) body of the bee, which provides vibration, and (2) removable and reusable ice wings, which provide the cold sensation. The body of the bee is powered by two alkaline AAA batteries, which could last for approximately 20 hours. There is a manual switch on the top part of the body of the bee that is used to activate and deactivate the vibration. The removable set of ice wings contain a total of 18 grams of ice and can stay frozen for about 10 minutes when exposed to room temperature. The Co-I who will be applying the Buzzy® device will follow the manufacturer's (MMJ Labs, Atlanta, Georgia, USA) recommendations and will (1) retrieve the set of ice wings from the freezer in the Preop Unit immediately before the peripheral intravenous catheter procedure, (2) insert the ice wings through the elastic bands fixed on the back of the Buzzy® device, (3) secure the Buzzy® device on the subject's arm with a reusable tourniquet, about 3-5cm proximal to where the peripheral intravenous catheter will be inserted, (4) turn the manual switch of the device on, (5) clean and prepare the area where the peripheral intravenous catheter will be inserted, (6) insert the peripheral intravenous catheter approximately 60 seconds after the Buzzy® device was applied, (7) keep the device turned on throughout the procedure, until at least the needle is removed, (8) remove the Buzzy® device and clean both components of the device (body of bee and ice wings) with a disinfectant cleaner, (9) and place the ice wings back in the freezer of the unit for a subsequent procedure.

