Control group - *Intradermal lidocaine 2%*: Subjects in this group will have the intradermal lidocaine 2% administered to them. An individual vial of Lidocaine 2% will be utilized per subject. The lidocaine will be drawn up into a 3cc syringe, using a 25G needle. The Co-I will apply a reusable tourniquet to the subject's arm about 3-5cm proximal to where the peripheral intravenous catheter will be inserted. The area where the peripheral intravenous catheter will be inserted will be cleaned with an alcohol wipe. Lidocaine will then be injected intradermally, forming a small wheel underneath the skin. Within about 60 seconds of the intradermal injection, the peripheral intravenous catheter will be inserted. The remains of the lidocaine, lidocaine vial, needle, and syringe will be properly disposed into the sharps container.

The Co-I will fill out the top part of the questionnaire that is found below and ask the subject to fill out the bottom half of the questionnaire. The subject will then place the questionnaire into an envelope, without revealing the answers to the Co-I. This way the subject may feel more comfortable answering the questionnaire truthfully.

Once all subjects are enrolled, the data from the questionnaires will be entered into an excel sheet by one of the Co-I's. Data entry will be re-checked by another research team member to assure accuracy of data entry. Once data entry is complete, one of the Co-I's will perform the statistical analysis and the statistical analysis will be re-checked by a second research team member.

[Please note that we are aware that because of the current COVID-19 pandemic, most non-COVID-19 related studies are being placed on hold to minimize unnecessary interactions with patients. However, we would appreciate consideration of this study being done now since all the people that will be obtaining consent and conducting the study will be the essential personnel that will either way (regardless of whether the study will be taking place) will be taking care of these patients and placing those peripheral intravenous catheters. We believe that in such difficult times, any possible pain relief would be a significant benefit for patients. Furthermore, partaking in this study could be a nice distraction for these patients during these difficult times in the world.]

Below is the questionnaire that will be filled out for every subject:

Buzzy vs Intradermal Lidocaine for Peripheral Intravenous Cannulation in Adults

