2. *Include specific details of reporting procedures for:*
 - a. Deaths, life-threatening events, pregnancies: N/A
 - b. Other SAEs: N/A
 - c. Other AEs: N/A
 - d. Other UPS: N/A

H.3 Reportable New Information

Check to confirm that reportable new information will be reported to the IRB per the Tufts Health Sciences IRB's [Reportable New Information policy](#). If your reporting plan to the IRB differs from the IRB's policies, please describe it in detail or specify where this information is in the protocol:

I. Statistical Considerations

I.1 Study Endpoints

1. *Describe the primary and secondary study endpoints:* Primary study endpoint: Pain rating of the peripheral intravenous catheter insertion; Secondary study endpoint: Satisfaction rating of the peripheral intravenous catheter insertion
2. *Describe any primary or secondary safety endpoints:* N/A

I.2 Statistical Analysis

1. *Describe the statistical analyses that will be performed for this study:* Continuous variables will be analyzed via the Student's t-test and presented as mean +/- standard deviation. Categorical data will be analyzed via Chi-square test and presented as number and percentages. The intention-to-treat analysis will be used in this study. A P-value <0.05 will be considered statistically significant.
2. *Provide a power analysis:* Since there is currently no published study available comparing the two interventions that we plan on studying, we chose the study sample size based on the sample size rule of thumb for medical trials.¹³ The purpose of this study is to conduct a preliminary pilot trial for a potential future main trial designed with 90% power and two-sided 5% significance.

I.3 Number of Subjects

1. *Specify the number of subjects to be enrolled in total across all sites:* or N/A this is not a multicenter study.
2. *Specify the number of subjects to be enrolled at the Tufts site. Subjects who sign an ICF are considered “enrolled”. For studies that have a separate screening ICF, this number is the number of subjects who sign a screening ICF:* The goal will be to have a total of 30 subjects sign an ICF and complete the study based on the previously published sample size rule of thumb for medical trials.¹³

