 - a. *Provide the rationale for enrolling this number of subjects at the Tufts site:* Although unlikely, subjects might sign ICF and then change their mind within a few minutes while the research team member is preparing to perform the peripheral intravenous catheter insertion. To ensure we have 30 subjects complete the study, we will enroll up to 40 subjects in this trial.
 - b. *Estimate the number of subjects expected to be enrolled at the Tufts site (i.e. sign the screening or study ICF) as well as the number needed to complete the study at the Tufts site:* Subjects will only be enrolled in the study for the duration of the peripheral intravenous catheter insertion procedure and the time it takes to answer the questionnaire; therefore, in theory, only one or two subjects will be enrolled at the same moment.
 - c. *If a large number of withdrawals and/or dropouts is expected, explain why:* N/A

I.4 Data Management

1. *Describe the data analysis plan, including descriptions of the data:* The only data that will be collected is what is described in the questionnaire above.
2. *Provide a power analysis:* As described above, since there is currently no published study available comparing the two interventions that we plan on studying, we chose the study sample size based on the sample size rule of thumb for medical trials.¹³ The purpose of this study is to conduct a preliminary pilot trial for a potential future main trial designed with 90% power and two-sided 5% significance.
3. *Describe the steps that will be taken to secure the data (e.g., training, authorization of access, password protection, encryption, physical controls, certificates of confidentiality, and separation of identifiers and data) during storage, use, and transmission:* Data will be collected in an envelope and stored in a locked cabinet in the PI's office. Only the research team members will have access to the data for analysis purposes. Data will not have subject identifying information on it.
4. *Describe any procedures that will be used for quality control of collected data:* Data entry will be confirmed by two research team members.
5. *Describe how data and specimens will be handled study-wide as follows:*
 - a. *What information will be included in that data or associated with the specimens:* Please see section “F.2 Procedures” for the data that will be collected. No specimens will be collected.

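### Intention-to-treat is promised, but a subject who leaves after allocation would give no rating; the expected effect is small and cheap to prevent

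*Combined protocol and SAP*

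**What the plan says.** - **Analysis set (I.2).** "The intention-to-treat analysis will be used in this study". The set is not defined, and no rule is given for a missing rating.
- **Allocation (F.2).** If the patient consents, "then the Co-I will follow the randomization sheet with which pain-relieving technique to be administered to the patient". No step is described between consent and the sheet. The preparation that F.2 goes on to describe depends on the arm: for Buzzy, "retrieve the set of ice wings from the freezer in the Preop Unit immediately before the peripheral intravenous catheter procedure"; for the control, "The lidocaine will be drawn up into a 3cc syringe, using a 25G needle".
- **Withdrawal (D.3).** The form asks about procedures at withdrawal, "including the possibility of partial withdrawal from study intervention with continued data collection". The answer is "There will be no partial withdrawal from the study", followed by "Either the patient will take part in the study, which is just for the duration of the peripheral intravenous catheter insertion and the questionnaire" or not at all.
- **Numbers (I.3).** The goal is 30 subjects who sign and complete. Up to 40 may be enrolled because, although unlikely, "subjects might sign ICF and then change their mind within a few minutes while the research team member is preparing to perform" the insertion. The item on a large number of dropouts is marked N/A.
- **Data (I.4).** The questionnaire is the only data source, so a subject who leaves before completing it contributes no outcome.

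**The concern.** Each of these provisions is reasonable alone. Together they leave a window in which the promised analysis cannot be carried out. A subject who leaves once the sheet has been consulted has been allocated and so belongs in an intention-to-treat comparison, but D.3 provides no route to a rating. Recruitment then continues towards 30 completers, so a later subject in effect takes that place, and the analysis compares completers.

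That matters only if the losses differ by arm and the leavers would have rated pain differently from those who stayed. Subjects cannot be masked to the technique, and one technique adds a needle stick, so balanced loss is not guaranteed. What is at stake is the pain comparison between arms, which is the primary aim and is to be tested at P<0.05.

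**Working it through.** **The plan's own figures.** No dropout rate is stated. Working back from 40 enrolled and 30 complete, the ceiling tolerates 1 - 30/40 = 25% loss, and 30/(1 - 0.25) = 40. This is the room allowed, not a forecast.

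**Order of events.** The sequence in F.2 is consent, sheet, technique, catheter. I.3 places possible exits during preparation for the insertion. The arm-specific preparation must follow the sheet, so an exit during it comes after allocation. Preparation common to both arms could come earlier, and I.3 does not say which kind it means. Exits after allocation are therefore possible but not stated.

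**Assumptions** (none is given in the documents):
- k = 1 or 2 losses after allocation, all in one arm.
- Leavers' ratings would have differed from stayers' by d = 0.5 or 1 SD.
- 30 completers, and a two-sided 5% Student's t-test with 28 degrees of freedom.

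**Formulas**, in SD units:
- Shift = d × k / (number allocated in the losing arm).
- SE of the difference = √(1/n1 + 1/n2), on completers.
- Type I error from the noncentral t distribution, with noncentrality = shift/SE.

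| k | Allocated | Complete | d | Shift | SE | Shift/SE | Type I error |
|---|---|---|---|---|---|---|---|
| 1 | 16 v 15 | 15 v 15 | 0.5 | 0.031 | 0.365 | 0.09 | 0.0508 |
| 1 | 16 v 15 | 15 v 15 | 1 | 0.063 | 0.365 | 0.17 | 0.0531 |
| 1 | 15 v 16 | 14 v 16 | 0.5 | 0.033 | 0.366 | 0.09 | 0.0509 |
| 1 | 15 v 16 | 14 v 16 | 1 | 0.067 | 0.366 | 0.18 | 0.0536 |
| 2 | 17 v 15 | 15 v 15 | 0.5 | 0.059 | 0.365 | 0.16 | 0.0528 |
| 2 | 17 v 15 | 15 v 15 | 1 | 0.118 | 0.365 | 0.32 | 0.0612 |
| 2 | 16 v 16 | 14 v 16 | 0.5 | 0.063 | 0.366 | 0.17 | 0.0531 |
| 2 | 16 v 16 | 14 v 16 | 1 | 0.125 | 0.366 | 0.34 | 0.0626 |

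Example, last row: 1 × 2/16 = 0.125; √(1/14 + 1/16) = 0.366; 0.125/0.366 = 0.34.

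Simulation with the would-be leavers kept in the other arm's mixture gave 0.050-0.053 for one loss and 0.052-0.061 for two. Losses before allocation, or equal losses of the same kind in both arms, give no bias.

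**SD for sizing the later trial.** The pooled SD of completers relative to that of all allocated subjects is √((1+v)/(2v)), where v = 1 + p(1-p)d² and p = k/allocated. It is understated by 0.4-1.5% with one loss and 0.6-2.5% with two. With 28 degrees of freedom, the 95% confidence range for the true SD around its estimate runs from -21% to +35%, so this effect is immaterial.

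**The case against.** The strongest reply is that almost nothing is at stake. The plan calls these exits unlikely. Patients hear about both techniques and about random assignment before consenting, which should screen out those unwilling to have either. One loss barely moves the error rate, and a shift of at most 0.07 SD compares with a 95% half-width for the difference of 2.048 × 0.365 = 0.75 SD. The study is a pilot, and the SD it may supply is not materially affected. All of this stands, and it is why the point is minor. It does not remove the gap: I.2 still sets a significance test, and a rating not collected cannot be recovered.

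A second reply is that retaining decliners has a price. A decliner's rating may reflect a technique other than the assigned one. With one decliner of 16, 15/16 (94%) of the difference remains. At an assumed true difference of 0.5-1 SD, the 1/16 lost is 0.03-0.06 SD, about the size of the bias avoided. It pulls towards no difference, which is the unhelpful direction for a non-inferiority programme. This also stands, and is the reason to report the technique received.

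Three stronger readings are tempting but unsupported:
- **That I.3 makes over-enrolment a fault, or reuses allocation slots.** It says neither. Replacing subjects who leave before allocation does no harm.
- **That B.4 shows leavers have different options by arm, for instance that a Buzzy subject could leave and obtain lidocaine.** B.4 describes patients who never take part, and F.2 presents the usual technique as the provider's choice. An arm-specific incentive is possible but not documented, so the direction of any bias cannot be inferred.
- **That intention-to-treat is flatly contradicted.** It still governs subjects who complete without receiving the assigned technique as planned. The conflict arises only if someone leaves after allocation.

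**Conclusion.** The point holds as a minor, inexpensive improvement. The sections do not together secure the intention-to-treat comparison: an exit after allocation would leave no rating and turn the analysis into one of completers. Whether any such exit will occur is not settled by the documents.

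Under the stated assumptions the bias stays at about a third of a standard error or less, and the type I error at no more than 0.063. Both would grow if losses approached the permitted 10 and fell in one arm (0.083-0.185 at 10 of 25 allocated, with the same d), but nothing in the plan expects that.

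**What to change.** 1. **F.2.** Complete whatever preparation is common to both arms (such as choosing the site and having catheter supplies ready), reconfirm willingness to receive either technique, and only then consult the sheet. Replace only subjects who leave before that point. The steps within each technique stay as written. Little preparation is shared, so most of the gain comes from the reconfirmation.
2. **D.3.** Let a subject who declines the assigned technique after allocation still give the pain and satisfaction ratings for the insertion, if the subject agrees.
3. **I.2.** State that all allocated subjects with a rating are analysed in their assigned arm, that allocations are not reused, and that post-allocation losses and technique received are reported by arm. A sensitivity analysis for missing ratings is optional, and needed only if such losses occur.

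The ceiling of 40 may stay.

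**Cost.** A short amendment to D.3, F.2 and I.2 and to the consent form, IRB approval, and a briefing of the Co-Is; no extra subjects or visits. Some decliners may also refuse to give a rating. Ratings that are given carry the dilution described above, which must be weighed when the results inform a non-inferiority trial.

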According to the Center for Disease Control and Prevention (CDC), approximately 385,000 needle stick injuries and other sharps-related injuries occur annually by hospital employees. In other words, about 1,000 sharps injuries occur per day in American hospitals. Each time someone uses a needle, the risk of getting a needle stick injury increases.

Currently, at our institution, most nurses perform intravenous catheter insertion in adult patients without any prophylactic pain-relieving techniques. Anesthesia providers, at our institution, perform intravenous catheter insertion with either no prophylactic pain-relieving technique or with intradermal lidocaine injection prior to the performance of intravenous catheter procedure.

Based on the Gate Theory of Pain, which was first published in 1965 by Ronald Melzack and Patrick Wall in *Science*, non-painful signals, such as cold and vibration, can block pain signals from being interpreted as pain by the forebrain.¹² This is the theory behind why the device Buzzy® is effective in making patients feel more comfortable during peripheral intravenous catheter insertion. The use of this device is in theory beneficial because it eliminates the use of an additional needle and could therefore decrease the risk of accidental needle stick injury. Furthermore, the use of Buzzy® could potentially be financially beneficial because Buzzy® costs \$0.20 per use, while intradermal lidocaine 2% costs more than \$2 per use (the smallest size that lidocaine 2% comes in is a 2ml vial, which costs \$2 for our hospital, and each use of lidocaine 2% requires the use of a 25G needle and 3mL syringe, which both further increase the cost). In addition, Buzzy® is a reusable device, while the lidocaine vial, needle, and syringe are all one time use objects that continuously add to the global pollution problem.

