b. **Describe any potential bias in the selection of the active control such that there will be an unfair advantage for the investigational intervention. For example, is the active control treatment known to be significantly less effective in this study population than another treatment:** or N/A

c. **Check to confirm that the sample size and the randomization ratio for this active control study is ethically justified with regard to the number of participants who will be exposed to the risks of the study.**

B.2 Risks to Subjects

1. **List the reasonably foreseeable risks, discomforts, hazards, and/or inconveniences to the subjects related to their participation in the research, including risk of unintentional loss of confidentiality. Include a description of the probability, magnitude, duration, reversibility, and potential consequences of the risks. Consider physical, psychological, social, legal, and economic risks:** Subjects could in theory experience some discomfort from the cold pack/vibration in the Buzzy® device; however, based on data reported in previous literature, when Buzzy® has been used in pediatric patients, patients actually reported that the Buzzy® made them feel more comfortable.¹²⁻¹⁴ Also, there is always a risk of unintentional loss of confidentiality, but we will make every effort to prevent that from happening by keeping all data in a secure location.

2. **State which study interventions may have unknown risks:** or N/A

3. **State which study interventions may have risks to an embryo or fetus (if a subject is or becomes pregnant) or to a nursing infant of a study subject:** or N/A

4. **Describe risks to people other than the participating subject, e.g., risks to family members, friends, others or risks to the community:** or N/A

1. **Are there any risks to study investigators or staff performing the study procedures due to research with high risk populations (e.g. prisoners, intravenous drug users, patients with major psychiatric issues, etc.)?:**

Yes No

B.3 Potential Benefits to Subjects

1. **Describe the potential benefits that individual subjects may experience from taking part in the research. Include the probability, magnitude, and duration of the potential benefits:** The patients may have less discomfort and less anxiety during peripheral intravenous cannulation.

Check if there is no direct benefit.

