QUESTIONNAIRE

[figure not shown]
Questions to be answered by the Research Team:

Buzzy vs Intradermal Lidocaine for Peripheral Intravenous Cannulation in Adults

QUESTIONNAIRE

Questions to be answered by the Patient:

1) Please circle a number 0 to 10 in regard to how painful was the IV placement?

2) Please circle how satisfied you are with the IV placement?

Very Dissatisfied	Dissatisfied	Neither Satisfied nor Dissatisfied	Satisfied	Very Satisfied
(1)	(2)	(3)	(4)	(5)
				

2. *Is there a placebo control arm?*

Yes No

1. *Describe the following concerning pregnancy testing and birth control:*

- a. *What type of pregnancy testing and how frequently will be conducted on women of reproductive potential. If testing will not be conducted provide the reason:* N/A
- b. *What birth control methods women of reproductive potential will be instructed to use. If women will not be instructed about acceptable methods of birth control, clarify why:* N/A
- c. *What birth control methods men of reproductive potential will be instructed to use. If men will not be instructed about acceptable methods of birth control, clarify why:* N/A

2. *Describe the data that will be collected during the study and how the data will be obtained:*

- a. *If there are plans for long-term follow-up (once all research related procedures are complete), describe the data will be collected during this period:* or N/A

3. *Specify which procedures, tests, visits, etc. described above are part of usual standard of care at Tufts and which are performed solely for research purposes:* Insertion of intravenous catheter is part of the usual standard of care. The use of the Buzzy® device is not part of the current standard of care in adult patients at SEMC.

4. *Specify which tests are routinely performed for clinical care, but are providing data for the research, and which tests are only performed for research purposes:* No tests will be performed for the purposes of this study.

5. *For Humanitarian Use Device (HUD) uses provide a description of the device, a summary of how you propose to use the device, including a description of any screening procedures, the HUD procedure, and any patient follow-up visits, tests or procedures.* or N/A

F.3 Evaluations

Will you perform any laboratory tests for this study?

Yes No

F.4 Collection and Storage of Human Biological Specimens (Tissue Banking)

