2. *Describe the steps that will be taken to make the subjects feel at ease with the research situation in terms of the questions being asked and the procedures being performed. "At ease" does not refer to physical discomfort, but the sense of intrusiveness a subject might or might not experience in response to questions, examinations, and procedures (e.g. ensuring that subjects are comfortable with the research team members performing the study procedures):* Patients will be explained that they can ask any

questions that they would like and if anything does not feel right to them at any moment, they are encouraged to speak up immediately. The study members that will be obtaining consent are experiencing in obtaining consent, since they are anesthesia providers.

G.7 Provisions to Monitor the Study to Ensure the Safety of Subjects

1. *Describe the plan to periodically evaluate the data regarding both harms and benefits to assess subject safety as follows:*
 - a. *The data that will be reviewed, including safety data, untoward events, and efficacy data:* This study involves no to very minimal risk to subjects. No interim data analysis is planned at this time.
 - b. *Who will review the data:* N/A
 - c. *How the safety information will be obtained and documented (e.g., case report forms, by telephone calls with participants, printouts of laboratory results, etc.):* No adverse reactions are expected from this study; however, if, in theory, one were to occur, it would be reported in the form of a case report format.
 - d. *The frequency of data collection, including when safety data collection starts:* As described above, data will be collected per subject. Subjects remain enrolled in the study only for the duration of the peripheral intravenous catheter insertion and for the quick survey that will take place immediately after the peripheral intravenous catheter insertion. Since this study involves no to very minimal risk to subjects, if an adverse reaction occurs at any point, then it will be reported.
 - e. *The frequency or periodicity of review of cumulative data:* Data will only be analyzed once the study is complete.
 - f. *The statistical tests for analyzing the safety data to determine whether harm is occurring:* N/A
 - g. *Any conditions that trigger an immediate suspension of the research or other action for the research:* N/A

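### Harms are captured only by an undefined, unowned spontaneous-report route that conflicts with the questionnaire-only data rule, so they cannot be reliably counted or compared by arm

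*Combined protocol and SAP*

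**What the plan says.** On risk, B.2 item 1 states: "Subjects could in theory experience some discomfort from the cold pack/vibration in the Buzzy® device". The only other risk it lists is loss of confidentiality; it lists none for the lidocaine injection. The background in B.1 treats the extra needle as a hazard to staff: "Each time someone uses a needle, the risk of getting a needle stick injury increases".

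On reporting, G.7 item 1c says "No adverse reactions are expected from this study; however, if, in theory, one were to occur, it would be reported", in case-report form. Item 1d adds "if an adverse reaction occurs at any point, then it will be reported". Item 1e says of cumulative review: "Data will only be analyzed once the study is complete".

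On data, I.4 item 1 says "The only data that will be collected is what is described in the questionnaire above". The first patient item is "Please circle a number 0 to 10 in regard to how painful was the IV placement"; the second is a five-point satisfaction rating of the IV placement. The content of the research-team half is in a figure that is not shown. F.2 says of the form: "The subject will then place the questionnaire into an envelope, without revealing the answers to the Co-I". F.2 also starts data entry only after the last subject is enrolled, and F.1 allows up to a year for enrolment.

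These fields are N/A: who reviews the data, safety tests and suspension triggers (G.7 items 1b, 1f, 1g), the monitoring entity (G.7 item 2), adverse event definitions (H.1), reporting procedures (H.2) and safety endpoints (I.1 item 2).

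**The concern.** The plan makes a promise about harms and then provides no defined means of keeping it. A reaction gets into the record only if someone notices it, judges without a definition that it counts, and writes it up on a form the plan does not describe, outside the only data the plan says it will collect.

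The pilot is meant to inform a later non-inferiority trial of the device against lidocaine. The case for the device rests on patient comfort and fewer needle sticks as well as on cost and waste. If the pilot report carries a harm count, readers will want to know whether adults tolerated the device and how that compares with the injection. Under the plan as written, a low count could mean few reactions or few reports, and the two could not be told apart.

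**Working it through.** The plan states no harm rate or safety figure, so there is none to reproduce. The check sets the sections side by side, then asks what a zero count could show.

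**1. Promise against provision.** G.7 items 1c and 1d commit to reporting any reaction, at any time, in a document other than the questionnaire. I.4 item 1 allows no data other than the questionnaire. Both cannot hold as written. H.1, H.2 and G.7 item 1b, which could settle what counts, who writes it up and who reads it, are N/A.

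**2. What the visible items can show.** Both ask about the IV placement as a whole. A subject who found the cold unpleasant but the needle painless has no place to say so. In the lidocaine arm, each subject decides alone whether the sting of the injection belongs to the placement. A score of 4 may be cannulation pain, device discomfort, injection pain or a mixture.

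**3. Subjects who stop.** I.3 item 2a enrols up to 40 to obtain 30 completers, an allowance of 1 − 30/40 = 25%. The reason given is a change of mind during preparation, but nothing stops the same allowance being used when a subject cannot tolerate the technique. D.3 item 2 rules out partial withdrawal, and no step records the reason for stopping. As an illustration, two intolerance stops in an arm that is then filled to 15 would be 2/17 = 11.8% of those exposed, but 0/15 among completers.

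**4. What zero events would mean.** Inputs: 30 completers (I.3 item 2) at 1:1 (I.5), so 15 per arm if balanced; 20 per arm at the cap of 40.

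With complete collection, the exact upper bound after zero events in n is 1 − α^(1/n):
- n = 15: 1 − 0.05^(1/15) = 18.1% (one-sided 95%); 1 − 0.025^(1/15) = 21.8% (two-sided 95%).
- n = 20: 13.9% and 16.8%.

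The chance of seeing at least one event in 15 is 1 − (1 − p)^15. For assumed true rates p of 1%, 5%, 10% and 20% this is 14%, 54%, 79% and 96%. Common reactions would probably be seen if someone asked.

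With spontaneous capture, let c be the probability that a reaction is noticed and written up. The documents give no value. Zero reports bound the product p × c, so the one-sided bound on p is 18.1%/c (at most 100%):
- c = 1: 18.1%
- c = 0.5: 36.2%
- c = 0.25: 72.4%
- c ≤ 0.181: no information

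If c differs by arm, the comparison fails as well. With p = 20% in both arms and assumed c of 0.8 and 0.4, expected reports are 15 × 0.20 × 0.8 = 2.4 and 15 × 0.20 × 0.4 = 1.2, a twofold difference with no true difference. Such a gap is plausible because the staff know which technique they used, and one is familiar while the other is new to their adult patients.

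**The case against.** The strongest reply is that this is a 30-subject pilot of brief exposure with physicians present throughout. D.2 excludes Raynaud's syndrome, sickle cell disease, extreme cold sensitivity and broken skin at the device site. The device is on for about 60 seconds before insertion. Lidocaine injection is described as part of standard care at the hospital. The pilot's stated use is a baseline and a sample size for pain, not a safety claim, and a bound of 18% to 22% says little about tolerability. All of this stands. It is why a formal safety test is not warranted and why the point is a modest one.

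Three stronger readings are tempting, and the documents do not support them.
- A reader might infer that the plan guarantees zero reported harms. It does not: G.7 items 1c and 1d provide a route, though a passive one.
- A reader might infer that the form has no harms item. That cannot be established, because the research-team half is not shown, and a missing figure is not a gap in the plan. The existence of a separate case-report route does not prove what that half omits.
- A reader might infer that a run of reactions would reach nobody in time. A treating physician applies the technique, subjects are encouraged to speak up at once (G.6 item 2), and the same team gives the later anesthesia (G.1 item 4). What goes unread in the envelope is the patient's pain and satisfaction answers, not what the physician observes.

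The reply does not remove the conflict between G.7 and I.4, the absence of a definition or owner, or the unrecorded reasons for stopping. H.3 has an item on reporting new information to the IRB, but it too depends on someone noticing.

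**Conclusion.** The concern holds as a matter of capture and interpretation. Harm reporting is spontaneous, undefined and unowned; G.7 conflicts with I.4, H.1 and H.2; and the visible patient items cannot isolate the one physical risk that B.2 names. Harms are likely to be under-counted and cannot be compared by arm. A zero count with 15 per arm would support an upper bound of 18% (one-sided) or 22% (two-sided) only if every reaction were captured. With capture unknown, no bound can be stated.

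This rests on balanced arms of 15 and on the research-team half of the form having no solicited harms items. If it has them, the collection gap narrows, but the missing definition, reviewer and planned reporting remain. The true rates and capture probabilities used in the working are assumptions. The pain comparison itself does not depend on any of this. The change is worth making because it is cheap.

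**What to change.** 1. Reconcile G.7 items 1c and 1d with I.4 item 1, H.1, H.2 and I.1 item 2, so that the plan says in one place what counts as a reaction, where it is written and who reads it.
2. Unless the research-team half already has them, add solicited items for both arms:
   - on the patient half, one item on discomfort from the technique itself (device or injection), separate from the IV placement;
   - on a sheet kept out of the sealed envelope, yes/no boxes for the Co-I: skin or injection-site reaction; technique stopped or refused because of intolerance, including subjects later replaced; staff needle stick. The last is a staff event and should be tabulated apart from subject harms.
3. Record these against the randomization number, which keeps the data free of identifiers as I.4 item 3 requires.
4. Name the PI in G.7 item 1b and H.2 as reviewer of each ticked box.
5. Report counts by arm descriptively with exact confidence bounds, using everyone in whom the technique was started as the denominator. Add no formal safety test.
6. Separately, correct the support cited in B.2. It cites references 12 to 14 for pediatric comfort with the device, but the list ends at 13; reference 12 is a gate-theory paper and 13 a pilot sample-size paper.

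The cost is about a minute per subject and a short amendment, with no extra staff because the same physicians already attend the subject. The downside is that the report could state that no adverse events occurred only alongside a wide bound.
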